4.2.4. Change and Percent Change from Baseline

The change and the percent change from baseline in a measure at a post-baseline visit will be derived as:

- Change = (Score at the Post-Baseline Visit) – (Baseline Score)
- Percent Change from Baseline = $100 \times \text{Change} / (\text{Baseline Score})$

4.2.5. IOP Response Endpoints and Response Rate

At each post-baseline visit (Week 2 or Week 6), the following response endpoints are defined:

- $\geq 20\%$ Reduction Response: the percent reduction from baseline in mean diurnal IOP in the study eye is at least 20%.
- $\geq 25\%$ Reduction Response: the percent reduction from baseline in mean diurnal IOP in the study eye is at least 25%.
- $\geq 30\%$ Reduction Response: the percent reduction from baseline in mean diurnal IOP in the study eye is at least 30%.
- ≤ 18 mmHg Response: the mean diurnal IOP in study eye is equal or below 18 mmHg.

4.3. Safety-Related Definitions

4.3.1. Adverse Event

Under Protocol 011712IN, an AE is defined as any untoward medical occurrence (e.g., sign, symptom, disease, syndrome, intercurrent illness) that occurs in a study subject, regardless of the suspected cause and regardless of timing of study medication administration. An *on-study* AE can occur any time after the date of informed consent through the last study visit. An AE will be considered as *treatment-emergent* if the AE occurred on or after the treatment start date up to the 2 days after treatment end date. Treatment-emergent AEs are a subset of on-study AEs. Both on-study and treatment-emergent AEs will be recorded, but only treatment-emergent AEs will be tabulated.

The severity of each AE will be graded by the Clinical Investigator as Mild, Moderate, or Severe.

Each AE will be classified into a system organ class (SOC) and coded to a preferred term (PT) using Medical Dictionary for Regulatory Activities (MedDRA), version 21.1 published in 2018.

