7. DISCONTINUATION OF STUDY INTERVENTION AND SUBJECT DISCONTINUATION/WITHDRAWAL

7.1. Discontinuation of Study Intervention

Subjects may be discontinued from study drug administration for adverse events, non-compliance with study treatment, protocol deviation, lack of efficacy, withdrawal by subject, lost to follow-up, study termination, or other reasons. The investigator or Santen medical monitor may discontinue a subject from further study drug administration for reasons related to the best interest of the subject.

Subjects should be encouraged to continue participating in all remaining follow-up study visits/procedures on an observational basis when study drug administration is discontinued prior to the last scheduled visit (Visit 4).

If subjects agree to continue the study participation, then to the extent possible, all procedures for Early Termination will be performed on the day of early drug discontinuation or at the earliest opportunity.

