8.3.1. Time Period and Frequency for Collecting AE and SAE Information

All SAEs will be collected from the signing of the ICF until the subject withdrawals or completes the scheduled exit visit.

All AEs will be collected from the signing of the ICF until the subject withdrawals or completes the scheduled exit visit.

All SAEs and ESIs will be recorded and reported to Santen or designee immediately and under no circumstance should this exceed 24 hours, as indicated in [Section 10.2](#). The investigator will submit any updated SAE or ESI data to Santen within 24 hours of it being available.

Investigators are not obligated to actively seek AE or SAE after conclusion of the study participation. However, if the investigator learns of any SAE, including a death, at any time after a subject has been discharged from the study, and he/she considers the event to be reasonably related to the study intervention or study participation, the investigator must promptly notify Santen.

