9.3.7. Safety Analyses

All safety analyses will be performed on the Safety Population by each actual treatment received.

Safety of DE-117 will be primarily assessed by AEs, BCVA and evaluation with slit-lamp biomicroscopy and indirect ophthalmoscopy.

Besides the overall summary of AEs, subjects with any AE(s) will be tabulated by system organ class (SOC) and preferred term specified in MedDRA dictionary. They will also be tabulated by SOC, preferred term, and maximum severity. For AE tables, a subject who experienced multiple AEs within a SOC or preferred term will be counted only once at the maximum severity for that SOC or preferred term. SAEs will be tabulated similarly. Separate summaries for ocular AEs and non-ocular AEs will also be performed.

AEs leading to death, SAEs, and AEs leading to discontinuation, if any, will be listed separately. Events of special interest will be listed by type of event. For other safety assessments, descriptive summaries of observed score, change from baseline, whichever applicable, will be performed.

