4.1.2. Treatment Start and End Dates

Treatment start date is the date at which a randomized subject takes the first dose of the study medication.

Treatment end date is the date at which a randomized subject takes the last dose of the study medication. If the date of the last dose is missing, then

- The day before the Visit 4 (Week 6) will be considered the treatment end date for subjects who completed the study, and
- The day before the Exit Visit date will be used for subjects who prematurely discontinued from the study. If the Exit Visit date of a non-completer is not available, then the day before the last available visit date will be considered the treatment end date.

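### AEs starting more than 2 days after an early last dose are collected but tabulated nowhere, although the protocol tabulates subjects with any AE

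*SAP*

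**What the plan says.** SAP 4.3.1 sets two nested periods. An on-study AE "can occur any time after the date of informed consent through the last study visit". A treatment-emergent AE is an on-study AE that also qualifies "if the AE occurred on or after the treatment start date up to the 2 days after treatment end date". The consequence for reporting is explicit: "Both on-study and treatment-emergent AEs will be recorded, but only treatment-emergent AEs will be tabulated". SAP 9.1 then describes the AE, SAE and suspected-adverse-reaction tables, and separately lists AEs, SAEs, suspected reactions and ESIs.

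Collection runs longer than tabulation. Protocol 8.3.1 states: "All AEs will be collected from the signing of the ICF until the subject withdrawals or completes the scheduled exit visit". Protocol 7.1 foresees subjects who come off drug but remain in the study: "Subjects should be encouraged to continue participating in all remaining follow-up study visits/procedures on an observational basis".

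Protocol 9.3.7 describes the tables without a treatment-emergent limit: "subjects with any AE(s) will be tabulated by system organ class (SOC) and preferred term specified in MedDRA dictionary", with SAEs handled in the same way.

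**The concern.** The upper limit works differently for two kinds of subject. Someone who takes the Visit 4 dose leaves the study that day, so no collected day lies beyond the limit. Someone who stops drug early and stays, as the protocol encourages, can contribute weeks of AE collection that the tables ignore. SAP 4.3.1 gives no reason for choosing 2 days, and the SAP describes no table of post-treatment AEs.

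The safety objective is to compare BID with QD. SAP 6 plans no statistical testing of safety measures, so the descriptive tables carry that comparison. A late-onset AE, SAE or suspected adverse reaction in an early stopper would be visible only to a reader who goes through the listings, and the tables would not match the protocol's description of them.

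**Working it through.** The documents state no figure to reproduce; the check is a count of days.

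**Inputs**
- Window: treatment end date plus 2 days (SAP 4.3.1).
- End of collection: the exit or last study visit (Protocol 8.3.1; SAP 4.3.1).
- Visit 4: Day 43 ± 3, with the morning drop given in clinic after the 08:00 IOP and exit the same day (Protocol 8.1.5).
- Missing last-dose date: the end date becomes the day before Visit 4 for completers and the day before the exit visit for others. If the exit date is also unavailable, "then the day before the last available visit date will be considered the treatment end date" (SAP 4.1.2).

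**Formulas**
- Off-drug days collected = exit day − last-dose day
- Kept as treatment-emergent = min(2, off-drug days)
- Collected but untabulated = off-drug days − kept

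**Results**

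| Case | End of treatment | Exit | Off-drug days | Kept | Untabulated |
|---|---|---|---|---|---|
| Completer with Visit 4 dose recorded | Day 43 | Day 43 | 0 | 0 | 0 |
| Completer, end date set to day before Visit 4 | Day 42 | Day 43 | 1 | 1 | 0 |
| Early stop | Day 16 | Day 43 | 27 | 2 | 25 (Days 19–43) |
| Same, earliest exit in window | Day 16 | Day 40 | 24 | 2 | 22 |
| Same, latest exit in window | Day 16 | Day 46 | 30 | 2 | 28 |
| Later stop | Day 28 | Day 43 | 15 | 2 | 13 |
| Stop within 2 days of exit | Day 41 | Day 43 | 2 | 2 | 0 |

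The stop days are illustrations; the documents give no distribution of stopping times.

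**Does the missing-date rule add to the loss?** With imputation, the window closes at last visit − 1 + 2 = one day after the last visit. On-study AEs end at the last visit, so no on-study AE with onset on or after first dose is cut off.
- Last seen on Day 15: end date Day 14, window to Day 16, collection to Day 15. Nothing is lost.
- Seen only at Visit 2: the end date is the day before Visit 2, which precedes the first dose and is odd as a definition, but two days later is Day 2. Nothing is lost.

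The loss therefore needs a recorded last-dose date more than 2 days before the last visit.

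**Weight of one subject.** With about 50 per arm, 1/50 = 2 percentage points of incidence in a table row. That applies only if the subject has no other counted event in that row.

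**The case against.** Limiting the main AE table to the treatment period plus a short lag is a common convention, and much of the defence stands. Events on drug and on the first two days after it remain tabulated. So do events with a completely missing onset date (SAP 6.2.3). Nothing is lost when exit follows within 2 days of the last dose. SAP 9.1 lists all AEs, so no event disappears from the report. The protocol also leaves analysis detail to the SAP (Protocol 9 and 9.3.4). And early stoppers may start other IOP-lowering therapy, so a table running to the last visit would mix in events under other treatment.

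Four stronger readings are tempting, but the documents do not support them.
- *The cut-off biases the comparison towards no difference.* This would need more stopping in the BID arm and untabulated events in subjects not already counted. An AE that leads to stopping normally starts on drug and is counted. The documents give no stopping or AE rate by arm.
- *The 2 days never matter for completers.* If the end date is imputed as the day before Visit 4, the extension keeps Visit 4-day events. Protocol 6.2.2 can also be read as ending dosing before Visit 4. And under Protocol 4.4, a subject who stops drug but attends every visit is a study completer.
- *The imputation rule in SAP 4.1.2 makes the loss worse.* The count above shows that it removes no on-study AE.
- *Macular edema first seen at a late fundus examination is automatically excluded.* The window depends on when the event occurred, not on when it was found. Protocol 9.3.7 itself presents ESIs as listings.

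What the defence does not answer is the mismatch between collection and tabulation in subjects the protocol encourages to stay, or the difference from Protocol 9.3.7.

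**Conclusion.** The point holds in a narrow form. SAP 4.3.1 keeps out of every AE table any event that starts more than 2 days after a recorded last dose in a subject still under follow-up, while Protocol 9.3.7 describes tables of subjects with any AE. For a subject who stops on Day 16 and exits on Day 43, this covers 25 of 27 off-drug days (22 to 28 days untabulated across the Visit 4 window). For completers dosed at Visit 4 and for subjects who exit within 2 days of stopping, it covers none.

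The size in events cannot be computed: it depends on how many subjects stop early, how many stay, and what happens to them. Protocol 7.2 expects withdrawal from the study to be uncommon but gives no rate, and says nothing about how often drug is stopped by subjects who remain. Neither the number of events lost nor the direction of any between-arm bias is established. I would rate this as a change to consider: the expected effect is small and the events remain in listings, but the remedy is simple.

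**What to change.** In SAP 4.3.1, tabulate AEs with onset from first dose through the last study visit, flag those that start more than 2 days after the last dose, and present the AE, SAE and suspected-adverse-reaction tables with and without the flagged events. Equivalently, keep the 2-day tables as they are and add a through-last-visit set. Showing both avoids a dispute about the treatment-emergent convention. State in the SAP how this relates to the any-AE tables of Protocol 9.3.7, so that the two documents agree. The wording on the last dose in Protocol 6.2.2, Protocol 8.1.5 and SAP 4.1.2 should also be reconciled, because the treatment end date drives the flag. The imputation rule in SAP 4.1.2 needs no change to prevent loss of events.

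The cost is SAP wording, one derived flag and a second set of tables, settled before unmasking. The downside is small: some events arising off study drug, or under other IOP-lowering therapy, enter one set of tables, and the flag identifies those that start more than 2 days after the last dose. Tables for completers dosed at Visit 4 do not change.

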4. STUDY DESIGN

4.1. Overall Design

This is a randomized, double-masked, parallel-group, multi-center study. Subjects diagnosed with POAG or OHT who meet eligibility criteria at Visit 1 (Screening) will wash out their current topical IOP lowering medication(s), if any. After completing the required washout period, subjects will return for Visit 2 (Baseline, Day 1). Subjects who meet all eligibility criteria at Visit 2 (Baseline, Day 1) will be randomized to receive study medication for up to 6 weeks.

Approximately 100 subjects with POAG or OHT will be randomized in a 1:1 ratio to either:

- DE-117 ophthalmic solution 0.002% QD (20:00) and Vehicle QD (08:00), or
- DE-117 ophthalmic solution 0.002% BID (20:00 & 08:00)

This study will consist of a screening period of up to 35 days including a washout period of up to 28 days (+ 7 days window), and a 6-week double-masked treatment period.

At the screening visit (Visit 1), subjects will be screened against the inclusion and exclusion criteria. Eligible subjects will be instructed to discontinue use of all IOP-lowering medications, if any, as follows (up to +7 days is allowed):

- Miotics: 7 days
- Oral/topical Carbonic Anhydrase Inhibitors (CAIs): 7 days
- Alpha agonists: 14 days
- Alpha/beta agonists: 14 days
- Alpha antagonists (α 1 blocker): 28 days
- Beta antagonists (β blocker, including $\alpha\beta$ blockers): 28 days
- Prostaglandins Analogs (PGA): 28 days
- Rho kinase (ROCK) inhibitor: 28 days
- Combination drugs: The longest washout period of the individual component will be used.

During the required washout period, subjects who discontinue their current treatment may, if the investigator deems necessary, be treated with a short-acting IOP lowering agent, topical CAI, e.g., brinzolamide or dorzolamide eye drops, one drop twice daily. Topical CAI treatment must be stopped 1 week before the randomization at Visit 2 (Baseline, Day 1). An interim safety visit during the washout period (mid-washout visit: Visit 1a) may be performed if, in the investigator's opinion, a subject's IOP may be of concern during the washout period. If subjects are treated with a topical CAI during the washout period, a mid-washout visit (Visit 1a) is recommended.

Final eligibility will be determined at Visit 2 (Baseline) after all necessary washout from prior IOP lowering medications have been completed. Subjects who have not used any IOP lowering

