10.1.12. Publication Policy

The existence of this clinical study is confidential, and it should not be discussed with persons outside of the study. Additionally, the information in this document and regarding this study contains trade secrets and commercially sensitive information that is confidential and may not be disclosed unless such disclosure is required by federal or state law or regulations. Subject to the foregoing, this information may be disclosed only to those persons involved in the study who have a need to know, but all such persons must be instructed not to further disseminate this information to others. These restrictions of disclosure will apply equally to all future information supplied that is indicated as confidential. Information pertaining to this study will be published on www.clinicaltrials.gov.

The data generated by this clinical study are the property of Santen and should not be disclosed without the prior written permission of Santen. These data may be used by Santen now and in the future for presentation or publication at Santen's discretion or for submission to governmental regulatory agencies. Santen reserves the right of prior review of any publication or presentation of data from this study.

This study will be registered at ClinicalTrials.gov, and results information from this study will be submitted to ClinicalTrials.gov.

In signing this protocol, the Principal Investigator agrees to the release of the data from this study, and acknowledges the above publication policy.

10.2. Adverse Events: Definitions and Procedures for Recording, Evaluating, Follow-up, and Reporting

Table 7: Definition of AE

AE Definition

• An AE is any untoward medical occurrence in a patient or clinical study subject, temporally associated with the use of study intervention, whether or not it is considered related to the study intervention.• NOTE: An AE can therefore be any unfavorable and unintended sign (including an abnormal laboratory finding), symptom, or disease (new or exacerbated) temporally associated with the use of study intervention.

Table 7: Definition of AE (Continued)

Events Meeting the AE Definition

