
 Any abnormal laboratory test results (hematology, clinical chemistry, or urinalysis) or other safety assessments (e.g., ECG, radiological scans, vital signs measurements), including those that worsen from baseline, considered clinically significant in the medical and scientific judgment of the investigator (and not related to progression of underlying disease [glaucoma or ocular hypertension], unless judged by the investigator to be more severe than expected for the subject's condition). Exacerbation of a chronic or intermittent pre-existing condition including either an increase in frequency and/or intensity of the condition. New conditions detected or diagnosed after study intervention administration even though it may have been present before the start of the study. Signs, symptoms, or the clinical sequelae of a suspected drug-drug interaction. Signs, symptoms, or the clinical sequelae of a suspected overdose of either study intervention or a concomitant medication. Overdose per se will not be reported as an AE/SAE unless it is an intentional overdose taken with possible suicidal/self-harming intent. Such overdoses should be reported regardless of sequelae. “Lack of efficacy” or “failure of expected pharmacological action” per se will not be reported as an AE or SAE. Such instances will be captured in the efficacy assessments. However, the signs, symptoms, and/or clinical sequelae resulting from lack of efficacy will be reported as AE or SAE if they fulfill the definition of an AE or SAE.
Events NOT Meeting the AE Definition

 Any clinically significant abnormal laboratory findings or other abnormal safety assessments which are associated with the underlying disease, unless judged by the investigator to be more severe than expected for the subject's condition. The disease/disorder being studied or expected progression, signs, or symptoms of the disease/disorder being studied, unless more severe than expected for the subject's condition. Medical or surgical procedure (e.g., endoscopy, appendectomy): the condition that leads to the procedure is the AE. Situations in which an untoward medical occurrence did not occur (social and/or convenience admission to a hospital). Anticipated day-to-day fluctuations of pre-existing disease(s) or condition(s) present or detected at the start of the study that do not worsen.

Table 8: Definition of SAE

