
The investigator will assess severity for each AE and SAE reported during the study and assign it to 1 of the following categories:
 
 Mild: An event that is easily tolerated by the subject, causing minimal discomfort and not interfering with everyday activities. Moderate: An event that causes sufficient discomfort and interferes with normal everyday activities. Severe: An event that prevents normal everyday activities. An AE that is assessed as severe should not be confused with a SAE. Severe is a category utilized for rating the severity of an event; and both AEs and SAEs can be assessed as severe. 
An event is defined as 'serious' when it meets at least 1 of the predefined outcomes as described in the definition of an SAE, NOT when it is rated as severe.
 
For intermittent events, record the maximum severity of the individual events. For example, if a subject complains of intermittent headaches for one week and the severity of each headache ranges from mild to moderate, then the severity would be moderate. Record that the severity of the headaches ranged from mild to moderate in the comment section of the form.

Table 9: Recording and Follow-Up of AE and/or SAE (Continued)

Assessment of Causality

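### The SAP's treatment-emergent rule has no worsening clause, so a washout AE that worsens on drug is missing from the by-arm AE tables if it stays on its pre-dose record

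*SAP*

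**What the plan says.** SAP Section 4.3.1 makes an AE treatment-emergent "if the AE occurred on or after the treatment start date up to the 2 days after treatment end date". It adds that on-study and treatment-emergent AEs are both recorded, "but only treatment-emergent AEs will be tabulated". Worsening of an event already present is not mentioned.

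Four other places bear on this rule:

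- **Collection period.** Protocol Section 8.3.1: "All AEs will be collected from the signing of the ICF until the subject withdrawals or completes the scheduled exit visit". Protocol Section 4.1 describes a "screening period of up to 35 days including a washout period of up to 28 days", plus a 7-day window. AEs are therefore recorded before the first dose.
- **Definition of an AE.** Protocol Section 10.2, Table 7, covers a sign, "symptom, or disease (new or exacerbated) temporally associated with the use of study intervention". Among events meeting the definition it names "Exacerbation of a chronic or intermittent pre-existing condition including either an increase in frequency and/or intensity of the condition".
- **Recording.** Protocol Section 10.2, Table 9, says for intermittent events to "record the maximum severity of the individual events", with the range of severity noted as a comment. It dates the end of such an event by its last occurrence. Under follow-up, it sends later information to the CRF already completed for the event.
- **Missing dates.** SAP Table 6 treats an AE with a wholly missing date as treatment-emergent, and it does so in the row for the onset date.

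**The concern.** The safety of BID compared with QD is a stated objective, and AEs come first among the main safety assessments in SAP Section 9. A complaint such as headache or eye irritation that is mild in washout and worse on drug is a plausible effect of more frequent dosing. A rule that looks only at when the event began can miss it.

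Where such events are missed, the error runs one way: the tabulated counts can only be too low, and they are lowest relative to the truth in the arm with more on-drug worsening. SAP Section 4.3.1 applies the limit to all tabulated AEs. It therefore also reaches the overall summary in SAP Section 9.1 of serious events, suspected reactions and events leading to stopping study drug. Protocol Section 9.3.7 plans the AE tables without stating a treatment-emergent limit; the SAP adds it.

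If sites differ in whether worsening opens a new record, the AE counts also depend on site practice.

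**Working it through.** The plan gives no figure on this point. The check is to read the passages together and apply the date rule to an example.

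**1. What does the rule test?** SAP 4.3.1 uses the time at which the AE occurred. It does not use the word onset. SAP Table 6 is the only other place that assigns treatment-emergent status, and it does so through the onset date. In programming, the rule therefore becomes:

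treatment start ≤ onset ≤ treatment end + 2 days

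**2. What onset date does a worsening event carry?**

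| Place | Points to |
|---|---|
| Table 7, exacerbation is an AE | a new record dated at the worsening |
| Table 9, one maximum severity for an intermittent event | one record, with the grade raised |
| Table 9, end date is that of the last occurrence | one record spanning the episodes |
| Table 9, later information goes on the CRF already completed | one record, with the first onset kept |

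Table 7 speaks of a pre-existing condition. It does not say that an AE already recorded in washout receives a second record. The Table 9 follow-up instruction is not limited to intermittent events, but it does not mention worsening across the first dose.

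**3. Apply the rule.** The example is assumed: treatment from Day 1 to Day 42, AE onset 14 days before Day 1, worsening on Day 10. The window is Day 1 to Day 42 + 2 = Day 44.

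- One record, onset Day -14: -14 < 1, so it is not treatment-emergent and is in no AE table. The worsening survives only as a raised grade and perhaps a comment.
- New record, onset Day 10: 1 ≤ 10 ≤ 44, so it is treatment-emergent and tabulated.

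The same clinical course is counted or not counted according to a recording convention that neither document fixes.

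**4. Size.** From the design, 50 subjects per arm: 1/50 = 2 percentage points of an arm's AE incidence per subject missed. A count needs three rates that the documents do not give:

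missed subjects = 100 × p × w × s

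Here p is the share of subjects with an AE present at first dose, w is the share of those that worsen on drug, and s is the share of worsenings kept on the old record. As an assumption only, take p = 2% to 10% and w = 20% to 50%:

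- Low: 100 × 0.02 × 0.20 × s = 0.4s
- High: 100 × 0.10 × 0.50 × s = 5s

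With s = 1 this is 0.4 to 5 subjects in the trial, and with s = 0 it is none. The documents do not fix s, so 0.4 to 5 is a ceiling for these assumed rates and not an estimate.

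**The case against.** The strongest reply is that Table 7 already settles the matter. An exacerbation is an AE, so a site that enters it as one gives it an on-treatment date, and SAP 4.3.1 tabulates it. A reader might infer from the SAP alone that every washout AE that worsens on drug is left out of every AE table. The documents do not support that, because the omission depends on how the site records the worsening. What remains is that no text tells the site to open a new record for an AE already entered in washout, and Table 9 leans the other way.

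It can also be said that Table 9 does not prescribe a single record across the first dose. Its severity and end-date rules concern intermittent events, and its headache example covers one week. This is correct: Table 9 points to one record but does not require it. The eCRF completion instructions, which are not among the documents, may already address the question.

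Third, other displays show part of the information. SAP Section 9.1 lists AEs, serious AEs and suspected reactions with no stated treatment-emergent limit. SAP Sections 9.2 to 9.4 summarise worsening of slit-lamp, ophthalmoscopy and visual acuity findings, so redness would probably show as hyperemia. It would be wrong to infer that the event disappears from the report. But a listing gives no incidence by arm, and the graded examinations do not capture symptoms such as headache or irritation.

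Finally, the exposure is limited. The 35 days is a maximum, and subjects off IOP-lowering medication for 28 days may wait as little as 1 day (Protocol Section 4.1). SAP Section 6 plans no testing of safety measures, so no p-value is affected. Both points stand. They limit the size of the problem but do not remove the ambiguity.

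**Conclusion.** The point holds as a gap in the definition. The treatment-emergent rule is date-based with no worsening clause, and the documents leave open whether on-drug worsening of a washout AE receives its own date. When it stays on the existing record, the event is absent from the AE and suspected-reaction tables by arm, though not from the listings.

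This rests on reading occurrence as onset, which SAP Table 6 supports but SAP 4.3.1 does not state, and on at least some sites keeping worsening on the old record, which Table 9 makes likely but does not mandate. The number of subjects affected cannot be computed from the documents. Each one would be 2 percentage points of a 50-subject arm. Efficacy conclusions are untouched. The change is worth making because a comparative safety objective relies on these tables and the remedy is small.

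**What to change.** Two changes are needed together. A worsening clause cannot be programmed if the database holds only the first onset and a maximum grade.

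1. **SAP Section 4.3.1.** Define an AE as treatment-emergent if it starts, or increases in severity or frequency or becomes serious, on or after the treatment start date and up to 2 days after the treatment end date. This keeps the existing upper limit.
2. **eCRF completion instructions.** State that worsening after the first dose of an AE that began before dosing is entered as a new record with the date and severity of the worsening, intermittent events included. Explain how this fits with Table 7 and with the Table 9 rules on maximum severity and later information.

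The cost is one SAP sentence and a short eCRF instruction, plus a few extra AE records and slightly higher AE counts. Subjects are not double-counted, because SAP Section 9.1 counts a subject once per system organ class or preferred term. If the sponsor finds that Table 9 itself must be reworded, that is a protocol amendment needing ethics approval under Protocol Section 10.1.2; placing the rule in the eCRF instructions is meant to avoid this.
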